#### 4. Self-reported activity level and muscle function

##### (a) Lysholm Score (7)

Lysholm Knee Score is a questionnaire that examines knee-specific symptoms and function of daily living. It consists of eight items, with a total score ranging from 0 to 100 and a higher score indicates a better outcome with fewer symptoms of disability.

##### (b) International Knee Documentation Committee Subjective Knee Form (IKDC) (8)

IKDC is a self-reported questionnaire that measures symptoms, knee function and activity of daily living. The questionnaire consists of 10 questions, with a total score ranging from 0 to 100 and a higher score indicates greater knee function.

##### (c) Tegner Score (9)

The Tegner Activity Scale was used to assess activity level that related to sports on a scale of 0 to 10. Zero represents a low activity level and 10 represents the highest activity level.

##### (d) Physical Activity Questionnaire (10)

Level of physical activities during the past year will be evaluated with a validated Chinese version of the quantitative physical activity questionnaire adapted from Baecke et al.

## 5. Isokinetic muscle strength assessment

The dynamometer (Biomed System 4, Biomed Medical Systems Inc., New York, USA) will be used. Subjects will perform a standardized warm-up exercise (5 min cycling) followed by the test. Concentric/concentric contractions of knee extension/flexion will be tested at 60°/s and 180°/s (11). Subjects will be seated on the dynamometer chair with their hips flexed to 85°.

## 6. Knee laxity

### (a) Passive knee laxity

To measure the anterior-posterior knee laxity, the KT-1000 knee ligament arthrometer (MEDmetric Corp, San Diego, CA, USA) will be used. Manual force test will be applied until 30lb sound signal is activated. Three trials will be performed. A side difference of 3 mm or above is considered clinically relevant (12).

## 7. Biomechanics - Motion Analysis

The kinematics will be assessed by the skin marker-based motion analysis system (Vicon MX, Oxford, UK) with the lower-body marker setup, following the OSTRC standard protocol using 16-camera and 16 reflective skin markers.

### (a) Single leg hop (SLH) task

The SLH test will be performed as reported in the previous studies reported (13). Three trials will be performed on each leg followed by familiarization. The SLH will be deemed valid if the patients can achieve a maximal hop distance while maintaining their balance for at least 2s after landing.

### (b) Single leg squat (SLS) task

The subject will start at the upright standing position with their toes facing forward and squat down at a self-determined speed. Once the pre-assigned flexion angle is reached, subjects will be instructed to hold the position for 10 second. A trial will be invalid if the subject cannot maintain the proper balance. All participants will practice sufficiently to achieve the prescribed knee angle (40°-50° is acceptable).

## **Sample Size Estimation and Power Calculation**

For objective 1, when the sample size is 92, a bivariate correlation test will have 90% power to detect at the 0.050 level with a correlation coefficient of 0.3. The proposed sample size (150) will be sufficient to detect the difference and enables the fulfillment of objective 2 and 3 in this study (with an estimated 40% quadriceps strength deficit at 4-month post-op). For objective 2, when the sample size in each group is 30, a repeated-measure ANOVA (with three repeated measures) will have 90% power to detect at the 0.050 level, with an effect size of 0.35. (G\*Power 3.1.9.4).

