## Patient Recruitment & Eligibility

This is a prospective randomized, double-blinded placebo-controlled trial with all participants being recruited at the out-patient clinic of Prince of Wales Hospital. Participants are randomly assigned into either the Vitamin D intervention group or the placebo-controlled group through an online computer generator sequence at the time of admission to the out-patient clinic. 60 participants will be recruited, with 30 in each group. The study will be carried out in compliance with Declaration of Helsinki and the ICH-GCP. Ethical approval will be obtained from the local IRB before the study starts. Informed consent must be obtained from all patients in order to participate in the study.

Participants will be recruited according to the following criteria:

Inclusion Criteria	Exclusion Criteria

1) Aged 18-40 with unilateral ACL injury

2) Sporting injury with a Tegner score of 7

3) Pre-op serum vitamin D level <math><20\text{ng/ml}</math>

4) 4 months post-ACLR with serum Vitamin D level remained <math><20\text{ng/ml}</math>

5) LSI for quadriceps strength <math><70\%</math> of contralateral leg at 4-month isokinetic assessment

6) Both knees without history of injury/prior surgery

	

1) Concomitant bone fracture, major meniscus injury or full-thickness chondral injuries requiring altered rehabilitation program post-operatively

2) Pre-operative radiographic signs of arthritis

3) Metal implants that would cause interference on MRI

4) Non-HS graft for ACLR

5) Patient non-compliant to the rehabilitation program

6) Regular sunbed users

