### Outcome Measurements

#### 1. Anthropometric Measurement

Body Mass Index (BMI) would be calculated by the measured height and weight at 4 months post ACLR before vitamin D supplements, during the eighth week of vitamin D supplements, after the completion of 16 weeks vitamin D supplements, and 12-months post-operation. We would measure the waist circumference as well. Subcutaneous fat would be measured using skinfold techniques for the triceps brachii and biceps brachii.

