#### 3. Radiological Assessment

##### (a) Magnetic Resonance Imaging (MRI)

Muscle volumes of quadricep muscle are measured using a 1.5 or 3.0 Tesla MRI Scanner. Axial (3mm thick cut) T1W images are obtained from the anterior superior iliac supine (ASIS) to patella. Quadriceps muscles were manually outlined in each axial slice. Muscle volume was calculated by summing all of the slice-multiplied by slice thickness. The quality of the muscle is assessed by analyzing the fat content of the muscle mass using technique that has been reported by Reeder et al (6). Bilateral legs will be performed before the start of the vitamin supplementation (4 months post-op) and with the injured side repeated after the completion of the 16-weeks supplementation (8 months postop).The uninjured side will be used as reference for 'normal volume'.

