## **Data Processing and Analysis**

Data will be reported as the mean  $\pm$  standard error of the mean, except for non-normally distributed data which are reported as the median, minimum and maximum. All Statistical analysis will be performed using the Statistical Package for Social Sciences (SPSS) 25. Statistical significance will be set at  $p < 0.05$ . For objective 1, a bivariate Pearson's correlation will be used to detect correlation between serum vitamin D levels and muscle strength and size at 4-month post-op, controlled for anthropometric variables. For objective 2, data will be analyzed by a repeated-measure ANCOVA (Control vs vitD supplementation; with repeated measures at 4-, 8-, 12-month post-op; other anthropometric variables as covariance). Primary outcome would be quadriceps muscle strength. These statistical tests will be performed after checking the normal distribution with Kolmogorov-Smirnov test, otherwise, a non-parametric

equivalent will be used. The “Intention-to-Treat” principle will be followed for data analysis purposes on those who have completed 16-week treatment. “Protocol Evaluable Analysis” will also be conducted using the 80% compliance as the cut-off. This trial will be registered at a clinical trial registry ([ClinicalTrials.gov](https://www.clinicaltrials.gov)) before the study is implemented.

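### The 90% power statement names neither the tested term nor the correlation, and it best matches a group effect averaged over three visits, one of them before treatment

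*Protocol*

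**What the plan says.** Protocol, Patient Recruitment & Eligibility: "60 participants will be recruited, with 30 in each group".

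Protocol, Sample Size Estimation and Power Calculation, for objective 2: "a repeated-measure ANOVA (with three repeated measures) will have 90% power to detect at the 0.050 level, with an effect size of 0.35". The software is named ("G\*Power 3.1.9.4"), but not the procedure within it (between factors, within factors or interaction). No correlation among the repeated measures is given, and 0.35 is not translated into a strength difference.

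Protocol, Data Processing and Analysis: the model is a repeated-measures ANCOVA comparing the two groups, "with repeated measures at 4-, 8-, 12-month post-op; other anthropometric variables as covariance". The 4-month value is therefore one of the three outcomes, not a covariate. "Primary outcome would be quadriceps muscle strength". The section does not say whether the group main effect or the group-by-time interaction is the treatment test.

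Month 4 is before treatment. Anthropometric Measurement places its first assessment "at 4 months post ACLR before vitamin D supplements", and the MRI section says the same of its first scan. The 4-month isokinetic strength result is itself an inclusion criterion.

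**The concern.** A power figure can be used only if the reader knows which test and which effect it describes. The setting that most naturally returns 60 patients is a test that averages the group difference over all three visits. Randomisation makes the expected difference at the first of them zero, so a real effect at the two later visits is diluted by one third before it is tested.

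If that is the treatment test, the trial is well powered only for an effect half as large again as the 0.70 SD that effect size 0.35 suggests. A null result on quadriceps strength could then be reported as 90%-powered evidence against an effect that the test had only moderate power to detect.

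**Working it through.** **Inputs.** From the protocol: N = 60 (30 per group), m = 3 measures, alpha 0.05, effect size 0.35, visits at 4, 8 and 12 months, month 4 before treatment. Assumed: 0.35 is Cohen's f, so d = 2 × 0.35 = 0.70 SD for two equal groups; equal SDs and compound symmetry with correlation rho; no dropout.

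**Step 1: reproduce the stated 90%.** For the between-groups main effect, lambda = f² × N × m / (1 + (m − 1) × rho), with 1 and N − 2 df.

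- rho = 0.5: lambda = 0.1225 × 180 / 2 = 11.03, power 90.4%. At N = 58 it is 89.4%, so 60 is the smallest even total that reaches 90%.
- The result stays within 2 points of 90% only for rho of about 0.44 to 0.58. It is 95.5% at rho 0.3, 84.6% at 0.7 and 81.7% at 0.8.

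For the default within-between interaction, lambda = f² × N × m / (1 − rho), with 2 and 116 df. At rho 0.5, lambda = 0.1225 × 180 / 0.5 = 44.1 and power exceeds 99.9%. About 20 patients in total would suffice (88.4% at 18, 91.9% at 20). A two-sample t test at 0.70 SD gives 76%. The main effect with rho near 0.5 is thus the best match.

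**Step 2: the same 60 patients, with the effect present only after treatment starts.** Take differences of 0, 0.70 and 0.70 SD at months 4, 8 and 12.

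- Main effect: the average difference is (0 + 0.70 + 0.70) / 3 = 0.467 SD, so f = 0.233 and f² × 180 = 9.8. Hence lambda = 9.8 / (1 + 2 × rho).
- Interaction: half-differences around their mean are −0.233, 0.117 and 0.117, with root mean square 0.165. Then f² × 180 = 4.9 and lambda = 4.9 / (1 − rho).

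| rho | Main effect: lambda | Main effect: power | Interaction: lambda | Interaction: power |
|---|---|---|---|---|
| 0.3 | 6.13 | 68% | 7.0 | 64% |
| 0.5 | 4.90 | 59% | 9.8 | 80% |
| 0.7 | 4.08 | 51% | 16.3 | 96% |
| 0.8 | 3.77 | 48% | 24.5 | 99.5% |

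A simulation of 20,000 trials gave 58.5% and 47.9% for the main effect at rho 0.5 and 0.8, and 79.2% and 99.5% for the interaction.

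**Step 3: what 90% on the averaged test requires.** The average must be 0.70 SD, so each later visit needs 0.70 × 3 / 2 = 1.05 SD (at rho 0.5).

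**Step 4: a contrast that uses month 4 as baseline.** For the 8-month comparison adjusted for the 4-month value, SE = sqrt((1 − rho²) × 2/30) in SD units, with 57 df and a difference of 0.70 SD.

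- rho 0.3: SE 0.246, ratio 2.84, power 80%.
- rho 0.5: SE 0.224, ratio 3.13, power 87%.
- rho 0.7: SE 0.184, ratio 3.80, power 96%.

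**The case against.** The strongest reply is that the 90% is not a wrong number. It reproduces to within half a point, and what is missing is a specification, of which the exact model term is often left to a statistical analysis plan. The first part stands: this is not a calculation error. The second stands only in part. The sample-size justification is in the protocol and gives a definite power, and at the correlation that reproduces it, neither group term of the planned model has that power for 0.70 SD at both later visits.

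A reader might infer that the trial has only 48% to 59% power. The protocol does not support that. The range applies only if the main effect is the treatment test, which is not stated, and its lower end needs rho 0.8. At rho 0.3 the main effect has 68%. The interaction in the same model passes 90% between rho 0.6 (88%) and rho 0.7 (96%), although at rho 0.7 the main-effect calculation behind the stated figure would itself give 84.6%.

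A reader might also infer that the authors must have used the main-effect procedure. That is too strong. Less usual settings with an assumed departure from sphericity also come to about 90%: the SPSS-style effect size with epsilon 0.9 (90.4%), the Cohen-style one with epsilon 0.85 (90.1%), and the default interaction with rho 0 and epsilon 0.5 (90.4%). The procedure is inferred, and so is the reading of 0.35 as 0.70 SD at each later visit; the protocol promises no such difference.

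**Conclusion.** The point holds in a conditional form. The stated 90% cannot be tied to a test, because the term and the correlation are missing. Its best match is a main effect that includes a pre-treatment visit. For 0, 0.70 and 0.70 SD at rho 0.5, that test has about 59% power and the interaction about 80%, against 90% stated. Keeping the averaged test at 90% needs about 1.05 SD at both later visits.

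It does not follow that 60 patients are too few. The same patients give 80% to 96% for 0.70 SD at 8 months, adjusted for the 4-month value, over rho 0.3 to 0.7. The fault lies in the power statement and its link to the analysis, not in the number recruited.

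The protocol gives no correlation, so the range over rho is the honest answer. Dropout, for which the protocol makes no allowance, would lower every figure here.

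**What to change.** Rewrite the objective 2 sentence in Sample Size Estimation and Power Calculation so that it gives the treatment contrast, the assumed correlation with its basis, and the effect as a between-group difference at a named visit after treatment starts. Make Data Processing and Analysis test that same contrast.

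One possible wording: with 30 per group, the 8-month comparison of quadriceps strength adjusted for the 4-month value has about 80%, 87% or 96% power for a 0.70 SD difference if the correlation is 0.3, 0.5 or 0.7. If the group-by-time interaction is the intended test, give its power for a profile that starts at zero. If the averaged main effect is kept, state the lower power or the 1.05 SD requirement.

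The cost is a few sentences in two sections and no extra patients. The downside is that the stated power may be less favourable than 90%.

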## **Data Processing and Analysis**

Data will be reported as the mean  $\pm$  standard error of the mean, except for non-normally distributed data which are reported as the median, minimum and maximum. All Statistical analysis will be performed using the Statistical Package for Social Sciences (SPSS) 25. Statistical significance will be set at  $p < 0.05$ . For objective 1, a bivariate Pearson's correlation will be used to detect correlation between serum vitamin D levels and muscle strength and size at 4-month post-op, controlled for anthropometric variables. For objective 2, data will be analyzed by a repeated-measure ANCOVA (Control vs vitD supplementation; with repeated measures at 4-, 8-, 12-month post-op; other anthropometric variables as covariance). Primary outcome would be quadriceps muscle strength. These statistical tests will be performed after checking the normal distribution with Kolmogorov-Smirnov test, otherwise, a non-parametric

equivalent will be used. The “Intention-to-Treat” principle will be followed for data analysis purposes on those who have completed 16-week treatment. “Protocol Evaluable Analysis” will also be conducted using the 80% compliance as the cut-off. This trial will be registered at a clinical trial registry ([ClinicalTrials.gov](https://www.clinicaltrials.gov)) before the study is implemented.

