## **Objectives**

1. To determine the correlation between vitamin D status and quadriceps muscle strength at pre-op and at 4 months after ACLR.
2. To conduct a randomized-controlled trial to examine the therapeutic effects of vitamin D supplement on improving vitamin D deficiency status in patients with quadriceps muscle weakness after ACLR.
3. To examine the effect of vitamin D supplements on the quadriceps muscle strength for patients after ACLR.

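### Objective 1 adjusts the vitamin D–muscle correlation for anthropometric variables only; with sex not named, a difference between the sexes can appear as an association

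*Protocol*

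**What the plan says.** The first objective is "To determine the correlation between vitamin D status and quadriceps muscle strength at pre-op and at 4 months after ACLR". Data Processing and Analysis assigns it a bivariate Pearson analysis, described as the "correlation between serum vitamin D levels and muscle strength and size at 4-month post-op, controlled for anthropometric variables". No other covariate is named for this objective.

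Under Anthropometric Measurement the protocol lists BMI (from measured height and weight), waist circumference and arm skinfolds. Facilities and Major Equipment adds lean mass and body fat by bioelectrical impedance. Which of these enter the model is not said.

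Sex does not appear in the protocol, and the eligibility table does not restrict it. Age is limited to 18–40 and a Tegner score of 7 is required, but the protocol does not say whether those trial criteria bind the 150 patients of objective 1. A physical activity questionnaire is collected: "Level of physical activities during the past year will be evaluated".

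The scale of strength in the correlation is not stated. LSI appears only as an eligibility criterion. Muscle size is an MRI volume, with the uninjured leg as reference.

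**The concern.** Randomisation gives objective 1 no protection, so the adjustment set decides what the coefficient means. The protocol recognises that adjustment is needed and names the set itself, so this is not merely a detail left to an analysis plan.

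Absolute quadriceps torque and volume can be expected to differ markedly between men and women. If serum vitamin D also differs, pooling the sexes produces a correlation even when vitamin D and muscle are unrelated among men and unrelated among women. Hypothesis 2 holds that better vitamin D status will lead to better strength and size, so such a correlation would naturally be read as support for it.

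There is also a problem of wording: a bivariate correlation cannot be controlled for other variables. The analysis described has to be a partial correlation or a regression.

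**Working it through.** **1. The plan's own figure.** The protocol states "when the sample size is 92, a bivariate correlation test will have 90% power to detect at the 0.050 level"; the value assumed there is r = 0.3. By Fisher's z, n = ((z_α + z_power)/atanh(0.3))² + 3.
- One-sided α = 0.05: 92.4, and simulated power at 92 is 90.1%. The stated 92 reproduces.
- Two-sided: 112.7, so 113, with power of 83–84% at 92.
- At the planned 150, two-sided power for r = 0.3 is 96%, so sample size is not the difficulty here. The checks below use n = 150 and a two-sided 5% test.

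**2. Inputs.** From the documents: n = 150, p<0.05, and the anthropometric measures. Assumed, because the documents give nothing: the proportion of women p, the sex difference in strength d1 and that in vitamin D d2 (both in within-sex SDs and in the same direction), and zero association within each sex.

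**3. With no adjustment at all.** Let q = p(1−p). Then r = q·d1·d2 / √[(1 + q·d1²)(1 + q·d2²)].
- For p = 0.3, d1 = 1.5, d2 = 0.4: q = 0.21 and r = 0.126/√(1.4725 × 1.0336) = 0.102. The chance of p<0.05 is 23.7%.
- Over p = 0.3–0.4, d1 = 1.0–1.5, d2 = 0.2–0.6: r = 0.038–0.167 and the chance is 7.5–53.3%.

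This is not the planned analysis, which does adjust for anthropometry.

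**4. With adjustment for BMI, waist and skinfold (simulation, 30% women).** First assumed set of sex–anthropometry links (men: BMI 0.5 and waist 0.8 higher, skinfold 1 lower, in units of about 1 SD):

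| Vitamin D difference | Strength difference | Sex omitted | Sex added |
|---|---|---|---|
| 0.3 SD | 1 SD | 6.8% | 5.8% |
| 0.3 SD | 1.5 SD | 9.8% | 5.0% |
| 0.5 SD | 1 SD | 10.3% | 4.6% |
| 0.5 SD | 1.5 SD | 15.3% | 4.7% |

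A second assumed set (women: skinfold 1 SD higher, BMI 0.4 SD lower), with a 1.5 SD strength difference, gave 14.5% for a 0.4 SD vitamin D difference and 27% for 0.6 SD. Adding sex again returned the rate to about 5%. Together the range is roughly 7–27%.

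**5. If the covariates separate the sexes better.** Let D be the joint separation of the sexes by the covariates, in SDs. The sex variance left after adjustment is about q/(1 + q·D²), which replaces q in step 3. For p = 0.3, d1 = 1.5, d2 = 0.4:
- D = 1: q becomes 0.21/1.21 = 0.174, rate 18%.
- D = 2: 0.21/1.84 = 0.114, rate 11%.
- D = 3: 0.21/2.89 = 0.073, rate 8%.

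Height or lean mass in the model would push D upward.

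**6. If strength has no sex difference,** as might hold for LSI, the simulated rate with sex omitted is 4.6% and 5.3% for vitamin D differences of 0.3 and 0.5 SD. That is the nominal level.

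**The case against.** The strongest reply is that the documents do not show the problem exists. They give no proportion of women and no sex difference in vitamin D; if that difference is near zero, there is no bias. This stands: the size is conditional on assumptions, and only the exposure is established.

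Second, the anthropometric set is not enumerated. With height or impedance lean mass included, much of the sex difference in torque and volume is already carried. This stands as a reduction (step 5), not as a removal.

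Third, strength may be meant as LSI: eligibility uses it, and the sample size section speaks of a percentage strength deficit. That would bring the strength result to about 5%. But the analysis section does not say so, and it also names muscle size, for which no ratio is specified.

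Fourth, a reader might infer that the activity score should simply join the adjustment set because it is collected. The documents do not support that. The questionnaire covers the past year, so at 4 months post-op it mixes pre-injury and recovery activity, and activity at 4 months may be a consequence of weak quadriceps. Adjusting for it could introduce bias.

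Age is a weak confounder if the 18–40 limit applies to this sample, but adjusting for it costs almost nothing.

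**Conclusion.** The point holds as a minor improvement. The protocol names an adjustment set that omits sex in an unrandomised analysis of strength and muscle volume. Under the assumed differences (30% women, vitamin D 0.3–0.6 SD, strength 1–1.5 SD), the chance of a significant correlation with none within either sex is roughly 7–27% at n = 150. It is less with height or lean mass in the model, and about 5% for LSI strength.

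Three stronger readings go too far. A reader might take the 7.5–53% of step 3 as the error rate, but it belongs to an unadjusted correlation that is not planned. A reader might say that a significant result would reflect no real association, but objective 1 asks only for a correlation. One arising through sex is real; it is just not attributable to vitamin D. And a reader might infer that the trial's main result is at risk, but the randomised comparison of quadriceps strength does not depend on objective 1.

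**What to change.** In Data Processing and Analysis, replace the bivariate correlation for objective 1 with a partial correlation or linear regression adjusting for sex and age as well as the listed anthropometric variables. State whether strength is torque or LSI. Report the association within each sex as a check. Use the physical activity score only in a sensitivity analysis.

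The cost is one sentence and two degrees of freedom of about 150. With three anthropometric covariates, two-sided power for r = 0.3 is Φ(0.3095·√144 − 1.96) = 96.0%; with sex and age added it is Φ(0.3095·√142 − 1.96) = 95.8%. Age is already needed for eligibility, and sex is a single item to record.

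### Repeated-measures ANCOVA over three visits, in its standard form, discards a 16-week completer who misses only the 12-month strength test; a mixed model on the same data would keep them

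*Protocol*

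**What the plan says.** The Protocol's Data Processing and Analysis section fixes the method, the software and the visits. It states "For objective 2, data will be analyzed by a repeated-measure ANCOVA", comparing control with vitamin D, "with repeated measures at 4-, 8-, 12-month post-op", with anthropometric variables as covariates. On software: "All Statistical analysis will be performed using the Statistical Package for Social Sciences (SPSS) 25". The next statement after the model is "Primary outcome would be quadriceps muscle strength". On the analysis set, the intention-to-treat "principle will be followed for data analysis purposes on those who have completed 16-week treatment". No imputation, mixed model or rule for a missed visit appears.

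The MRI section places the end of treatment: the scan of the injured side is "repeated after the completion of the 16-weeks supplementation (8 months postop". The 12-month visit therefore falls about four months after the last tablet.

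Patient Recruitment & Eligibility says "60 participants will be recruited, with 30 in each group". The Sample Size section claims 90% power with 30 per group, three repeated measures and an effect size of 0.35. The number recruited is the number powered, with no allowance for loss.

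**The concern.** The usual repeated-measures procedure in SPSS (GLM) takes one row per person and removes any row with a missing repeated value. The 4-month value cannot be missing in an eligible participant, because strength at 4 months is an inclusion criterion. The case of interest is therefore someone who completed treatment, was tested at 8 months and did not return at 12 months. That person's end-of-treatment value of the primary outcome has been measured and is then not used.

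Two things are at stake. Precision is lost, including at 8 months, where the data exist. And the comparison becomes one among people who attended up to a year after surgery, which is biased if attendance is related to recovery. Neither sits well with an intention-to-treat label.

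This is distinct from limiting the analysis to 16-week completers. Correcting that wording would leave the deletion in place, and changing the model alone would leave the completers restriction in place.

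**Working it through.** **Inputs from the Protocol:** N = 60, 30 per arm; m = 3 measures; f = 0.35; alpha 0.05; stated power 90%.

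**Assumptions:** correlation between visits rho = 0.5, equal for all pairs; the test is the between-group effect averaged over visits; a fraction d of 10%, 15% or 20% misses only the 12-month visit, completely at random. The Protocol states none of these.

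**Step 1, the plan's own figure.** Noncentral F with 1 and N − 2 degrees of freedom and

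lambda = f² × N × m / (1 + (m − 1) × rho) = 0.1225 × 60 × 3 / 2 = 11.03.

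Power is 90.4%, which agrees with the stated 90%. On this reading, the stated figure needs 60 people with all three visits.

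**Step 2, after deletion.** The same formula with N × (1 − d):

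| Missing 12 months only | Analysed | lambda | Power |
|---|---|---|---|
| 10% | 54 | 9.92 | 87.1% |
| 15% | 51 | 9.37 | 85.1% |
| 20% | 48 | 8.82 | 82.8% |

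To end with 60 complete cases would take 60/0.9 = 67 recruited at 10% loss, 60/0.85 = 71 at 15%, or 60/0.8 = 75 at 20%, rounding up.

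**Step 3, a mixed model on the same people.** At rho = 0.5, regressing the 12-month value on the 4- and 8-month values leaves a residual variance of 2/3. Only that residual part is estimated from the reduced number; everything else uses all 60.

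- Three-visit average: complete-data variance 2/3, of which (1/9) × (2/3) is the residual part, a share of 1/9. Effective N = 60 / (8/9 + (1/9)/(1 − d)) = 59.3, 58.8 and 58.4.
- Change from 4 to 8 months: no 12-month value is needed, so effective N is 60, against 54, 51 and 48 after deletion.
- Change from 4 to 12 months: complete-data variance 1, residual share 2/3. Effective N = 60 / (1/3 + (2/3)/(1 − d)) = 55.9, 53.7 and 51.4.

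A simulation of 4,000 trials per setting gave mixed-model power of 89.2% at 10% loss and 89.1% at 20% loss for the three-visit average, against 90.0% with no loss.

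**Step 4, the model recommended below.** Step 3 keeps the 4-month value as an outcome so as to match the plan's power calculation. If 4-month strength is a covariate instead, the 8- and 12-month values have residual variance 1 − 0.25 = 0.75 and covariance 0.5 − 0.25 = 0.25.

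- Average of 8 and 12 months: variance (0.75 + 0.75 + 2 × 0.25)/4 = 0.5, residual part (1/4) × (2/3) = 1/6, share 1/3. Effective N = 60 / (2/3 + (1/3)/(1 − d)) = 57.9, 56.7 and 55.4.
- 8 months alone: 60.
- 12 months alone: share (2/3)/0.75 = 8/9. At 20% loss, effective N = 60 / (1/9 + (8/9)/0.8) = 49.1, against 48 after deletion.

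The pattern is the same: the gain is at 8 months and in the average, with little at 12 months.

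**The case against.** The strongest reply is that the Protocol never says listwise deletion. It names neither the SPSS procedure nor a complete-case set, and an analysis plan not seen here could impute before the ANCOVA. That stands as a limit: deletion is the default consequence of the named method, not stated text. It does not dispose of the point, because the Protocol has chosen the method, software and visits, and a better choice using the same data and software is available.

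The size is also open to challenge. Attrition, rho and the effect tested are not stated. At rho = 0.7 the plan's power would be 84.6% before any loss. If the planned test were the group-by-visit interaction with lambda = f² × N × m/(1 − rho), power at N = 48 would still exceed 99%; with lambda = f² × df2 it would be 92.5% at 60 and 84.9% at 48. The power losses are therefore illustrative. The loss of measured 8-month values under deletion does not depend on them.

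The section ties the ANCOVA to objective 2 (vitamin D status), while strength is objective 3. Reading it as the primary analysis is an inference, but a fair one: the primary outcome is named straight after it, and no other between-group analysis of strength is given. The Protocol does not single out 8 months as the primary time point.

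A reader might infer a definite bias, or put a figure on it. The documents do not support that: they give no attrition rate and no link between attendance and strength, and a double-blinded design offers no basis for assuming strength-related loss in one arm only. A reader might also infer that a mixed model removes any such bias. It does so only as far as the observed values explain the loss.

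**Conclusion.** The point holds in a limited form. In its standard form the specified analysis would discard measured end-of-treatment strength values from completers who miss only the 12-month visit, and the sample size leaves no room for it. With rho 0.5 and a between-group test, both assumed, 10% to 20% such loss takes power from 90% to between 87% and 83%; a mixed model stays near 89% for the three-visit average. Against the mixed model the gain is thus about 2 points at 10% loss and about 6 at 20%. It does little for the 12-month contrast and cannot recover an 8-month value that was never measured. Complete-case analysis is biased if attendance relates to recovery; no size can be given.

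This should be changed, but the trial would remain interpretable if it were not.

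**What to change.** In Data Processing and Analysis, replace the repeated-measures ANCOVA of strength with a linear mixed model for repeated measures, fitted with SPSS MIXED:

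- outcomes: every available 8- and 12-month strength value, participants analysed as allocated;
- terms: treatment, visit, treatment-by-visit, 4-month strength, and the anthropometric covariates already planned;
- unstructured covariance between visits.

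The cost is small. Data, visits and software do not change. The model relies on missing at random, which should be stated. The Sample Size section's power statement is for a repeated-measures ANOVA and should be described as an approximation for the new model. The restriction to those who completed 16 weeks needs its own correction; this change does not resolve it.
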